### METHODOLOGY

#### **Study Design**

This study utilized a quantitative, randomized controlled trial approach to evaluate the impact of a HBM based educational intervention delivered through WhatsApp on oral health knowledge and behaviors among adults with T2DM. Participants were randomly assigned into two groups: an intervention group that received HBM-based education and a control group that received an educational brochure that includes information on oral health.

#### **Study Population/Settings**

The study population includes patients with a confirmed diagnosis of T2DM, verified through diabetes clinic records, who are regular attendees at National

institute of diabetes and Endocrinology at Dow University of Health Sciences Karachi.

### **Sampling Technique and Randomization**

A convenience sampling technique was used to recruit participants from the outpatient diabetes clinic at DUHS. Patients who are present at the clinic for their routine appointments and meet the eligibility criteria was approached. They were informed about the study objectives and procedures, and those who agreed to participate was asked to provide written informed consent. After enrollment, participants were randomly assigned to either the intervention group or the control group, following a 1:1 allocation ratio. The randomization process was stratified based on three key characteristics including gender, educational level, and duration of diabetes, to ensure balanced distribution and to minimize potential bias.

Randomization was conducted using random number generator where each participant was assigned a random number, then participants were allocated equally into either Intervention Group which received HBM based education via WhatsApp or control Group which received an educational brochure. This study was single blinded in which participants were not informed about the presence of two distinct groups; they were only aware about receiving education related to oral health.

[figure not shown]

Figure 3.1. Flow diagram of patient selection and allocation into intervention and control groups

## Sample Size

Sample size was calculated using OpenEpi online software, based on two independent sample t-test by using mean and standard deviation of post intervention perceived susceptibility score

which were  $4.09 \pm 0.49$  in intervention group and  $3.64 \pm 1.01$  in control group in the study conducted by Malekmahmoodi et al. (2020)(7). A sample size of 49 achieved in each group, power 95% with a significance level (alpha) of 0.01. Total 98 patients have been recruited and divided into 49 patients in each group (two groups).

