## **Objectives of the study**

The objectives of the study are to evaluate the impact of a WhatsApp-based HBM intervention on oral health knowledge and behavior of individuals with T2DM and to compare the effectiveness of WhatsApp based education with the education given via brochures.

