## **Hypothesis**

Adults having T2DM who acquire HBM based educational intervention regarding oral health through WhatsApp will show a significant improvement in oral health knowledge and behaviors, as compared to those who receives the educational brochure.

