### **Health Belief Model Constructs:**

A theoretical framework which consists of perceived susceptibility, severity, benefits, barriers, self-efficacy, and internal and external cues to action, used to explain and predict oral hygiene behaviors.(7)

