## **Study Duration From date to date**

The study was conducted from July 2025 to December 2025, including participant recruitment, the delivery of the educational intervention, and the completion of post intervention assessments.

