## **Survey Instrument**

A structured, close-ended and self-reported questionnaire with a five-point Likert scale was used. The questionnaire was designed to measure HBM constructs (e.g. perceived susceptibility, severity, benefits, barriers, cues to action, and self-efficacy), awareness of oral health and oral hygiene related behaviors. A panel of four subject matter experts reviewed the instrument, including two dentists, a public health specialist and an endocrinologist. Each expert independently evaluated the questionnaire items by using a four-point relevance scale, ranging from "not relevant" to "highly relevant." Their ratings were used to calculate content validity indices, Items with poor expert agreement ( $I-CVI \leq 0.25$ ) were removed, while items with minor disagreement ( $I-CVI = 0.75$ ) were revised for clarity. Items with strong relevance ratings ( $I-CVI = 1.00$ ) were retained as it is in the final questionnaire. The  $S-CVI/Ave$  for the final instrument was 0.89, which indicates good content validity. The universal agreement index ( $S-CVI/UA$ ) was 0.83, indicating that 83% of the items received unanimous relevance ratings from all four experts.(15)

The final questionnaire consisted of three major sections, designed to assess oral-health knowledge, HBM constructs, and behaviors among individuals with Type 2 Diabetes. Section I comprised of 10 items assessing oral-health knowledge. Section II included the HBM constructs, which was subdivided into

seven domains: Perceived Susceptibility (7 items), Perceived Severity (10 items), Perceived Barriers (6 items), Perceived Benefits (6 items), Self-Efficacy (7 items), Internal Cues to Action (4 items) and External Cues to Action (5 items). Section III was focused on oral-hygiene behaviors, comprising 10 items which measured the frequency and consistency of participants' oral-health behaviors.

The Cronbach's alpha value of the final instrument was calculated after the pilot study in which 30 participants filled the questionnaire which was 0.783. (16)

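### The sample size section claims 95% power at alpha 0.01, but its own figures give about 59% two-sided (80% at 0.05), for a score outside the hypothesis.

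*Combined protocol and SAP*

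**What the plan says.** All references are to the combined protocol and SAP.

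- **Objectives of the study** sets out to evaluate the "impact of a WhatsApp-based HBM intervention on oral health knowledge and behavior of individuals with T2DM". **Hypothesis** states that patients given the WhatsApp education "will show a significant improvement in oral health knowledge and behaviors, as compared to those who receives the educational brochure". Both name knowledge and behaviour and nothing else.
- **Health Belief Model Constructs** describes the HBM domains as "used to explain and predict oral hygiene behaviors". Perceived susceptibility is one of these domains.
- **Sample Size** gives a calculation "based on two independent sample t-test by using mean and standard deviation of post intervention perceived susceptibility score", with values from an earlier trial: 4.09 (SD 0.49) against 3.64 (SD 1.01). It concludes: "A sample size of 49 achieved in each group, power 95% with a significance level (alpha) of 0.01". It does not say whether the test is one- or two-sided.
- **Survey Instrument** lists one knowledge score, seven HBM domains (internal and external cues counted separately) and one behaviour score.
- **Data Analysis Procedure** compares perceived barriers and behaviour between groups by t-test and the remaining scores by Mann-Whitney. It sets one threshold of 0.05 for all tests and mentions no adjustment.
- **Study Duration** reports the work as finished: "The study was conducted from July 2025 to December 2025".

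**The concern.** The document makes one power statement, and it has three faults.

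1. The claimed 95% at alpha 0.01 looks far too high for 49 per group and a difference of little more than half an SD.
2. It concerns a belief score, while the hypothesis concerns knowledge and behaviour.
3. It assumes a t-test at 0.01, while the analysis section applies a rank test at 0.05 to this score.

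A reader who accepts the statement would take a non-significant result as strong evidence against an effect of the planned size. The figures do not support that.

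The secondary point is labelling. With eight or nine scores tested at 0.05 and none called primary, a report could give prominence to whichever HBM domain came out significant.

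**Working it through.** **Inputs** (Sample Size): means 4.09 and 3.64, SDs 0.49 and 1.01, 49 per group, alpha 0.01, power 95%.

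- Difference = 4.09 − 3.64 = 0.45
- Sum of variances = 0.49² + 1.01² = 0.2401 + 1.0201 = 1.2602
- Standardised difference = 0.45 / √(1.2602/2) = 0.45/0.794 = 0.567

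**Can the plan's 49 be reproduced?** With n per group = (z_alpha + z_power)² × 1.2602 / 0.45²:

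| Alpha | Sides | Power | Calculation | n per group |
|---|---|---|---|---|
| 0.01 | two | 95% | (2.576 + 1.645)² × 1.2602/0.2025 = 110.9 | 111 |
| 0.01 | one | 95% | (2.326 + 1.645)² × 1.2602/0.2025 = 98.1 | 99 |
| 0.05 | two | 80% | (1.960 + 0.842)² × 1.2602/0.2025 = 48.8 | 49 |

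The stated alpha and power do not give 49. Two-sided 0.05 with 80% power does. Using a single SD at alpha 0.01 and 95% power does not help either: SD 0.49 gives 43 two-sided or 38 one-sided, and SD 1.01 gives 180 or 159.

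**Power with 49 per group.** z = 0.45 / √(1.2602/49) = 2.806.

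- Two-sided 0.01: Φ(2.806 − 2.576) = 59%
- One-sided 0.01: Φ(2.806 − 2.326) = 68%
- Two-sided 0.05: Φ(2.806 − 1.960) = 80%
- One-sided 0.05: Φ(2.806 − 1.645) = 88%

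The noncentral t distribution changes little: 57%, 67%, 79% and 87%. No combination reaches 95%.

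**Power under the test actually used.** The power of Mann-Whitney depends on the shape of the scores, which the documents do not give. Two assumed shapes were simulated with the same means and SDs and 49 per group:

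- Normal scores: about 76% at 0.05.
- Beta-distributed scores on the 1 to 5 range: about 43% at 0.05.

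The normal shape fits poorly. Scoring bounds the domain scores at 1 to 5, the analysis section says these scores were not normal, and a normal control distribution would put about 9% of scores above 5, since (5 − 3.64)/1.01 = 1.35. The beta shape is also only an assumption. The two figures illustrate how much the answer moves; they are not limits.

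**Unadjusted HBM domains.** If no score truly differs, each two-sided 0.05 test has a 2.5% chance of a significant result in favour of the intervention. For seven independent domains: 1 − 0.975⁷ = 16.2%. If the two cue domains are merged: 1 − 0.975⁶ = 14.1%. With a common correlation of 0.3, 0.5, 0.7 or 0.9 (assumed; the documents give none), the seven-domain figure is 0.137, 0.115, 0.089 or 0.057.

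**The case against.** **The hierarchy is already there in substance.** The objectives and hypothesis are confined to knowledge and behaviour, and the HBM domains are given an explanatory role. This stands. A reader might infer that a significant domain counts as much as knowledge or behaviour, or quote the chance of any significant result among all nine scores (20% favourable, 37% in either direction, if independent). The documents do not support that reading: the hypothesis claims nothing about any one of nine scores, and a domain alone cannot satisfy it. What is missing is an explicit label.

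**The trial is finished.** This also stands. A formal gate or Holm procedure chosen after data collection cannot give confirmatory error control, so none is asked for.

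**The 49 is sound and only the words beside it are wrong.** This is plausible, because 49 matches two-sided 0.05 and 80% power exactly. It is still an inference, and it leaves the sentence incorrect. The one-sided requirement of 99 lies close to the trial total of 98, but the section says 49 in each group, so that does not rescue it.

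**Part of the document was removed before review.** A primary label there cannot be ruled out. It would not mend the power statement.

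A reader might also infer that the trial is underpowered for its hypothesis, or that nobody calculated power for knowledge or behaviour. The documents show neither. They give no planning effect or SD for those two scores, and show only that no power is stated.

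**Conclusion.** The power statement is wrong as written. For a comparison of means with the section's own figures, 49 per group gives about 59% two-sided or 68% one-sided at alpha 0.01, and about 80% at two-sided 0.05, against the stated 95% at 0.01. This rests only on numbers in the Sample Size section and the usual normal approximation. The statement also concerns a score outside the objectives and hypothesis, and a test and alpha other than those of the analysis. Power under Mann-Whitney is uncertain, at about 43% to 76% under the two assumed shapes.

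The secondary point is a reporting gap. In the text available for review no outcome is labelled primary, and the unadjusted HBM domains carry about a 16% chance of at least one favourable false positive if independent, and less if correlated. This does not undermine the test of knowledge and behaviour. It limits what may be claimed from the domains.

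**What to change.** 1. Replace the power sentence in Sample Size with: *49 per group gives about 80% power at two-sided alpha 0.05 for a t-test comparison of mean perceived susceptibility, a score outside the hypothesis. Power under the Mann-Whitney test actually used depends on the score distribution (about 43% to 76% at 0.05 in simulations with bounded beta and normal shapes, both assumptions). No power is stated for knowledge or behaviour.*
2. State in Data Analysis Procedure that the hypothesis is judged on knowledge and behaviour only.
3. Report the HBM domains, the within-group comparisons and the subgroup tests as exploratory.
4. Disclose that these labels were set after data collection.

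**Cost:** wording and a disclosure, with no new patients or data. The stated power becomes less favourable, no confirmatory claim can be made for the HBM domains, and the labels cannot be called prespecified.

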## **Data Analysis Procedure**

Data were analyzed through a statistical package for Social Sciences (SPSS) version 26. Frequency and percentages were reported for qualitative variables. Mean and standard deviations were reported for normally distributed quantitative variables while median and interquartile ranges were reported for non-normally distributed quantitative variables. Normality of quantitative variables were assessed using Shapiro-wilk's test of normality. The Independent sample t-test was conducted to compare the mean scores of perceived barriers and behavior between the intervention and control groups. For all other constructs, which were not normally distributed, the Mann-Whitney U test was applied. For within-group comparisons of pre and post scores of behaviors and perceived barriers, the Paired sample t-test was used. The Wilcoxon signed rank test, was used for the remaining variables that were not normally distributed. Stratification was carried out based on gender, diabetes duration, and education level to see the effect of these modifiers on outcome (control vs. intervention) using Chi-square test. A p value less than and equal to 0.05 was considered as significant.

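### With 49 patients per group the trial does not have 95% power at alpha 0.01; it has about 80% at two-sided 0.05 and about 59% at two-sided 0.01

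*Combined protocol and SAP*

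**What the plan says.** The Sample Size section names the software and the test: "Sample size was calculated using OpenEpi online software, based on two independent sample t-test". The quantity used is the "mean and standard deviation of post intervention perceived susceptibility score" from an earlier published trial, 4.09 (SD 0.49) in the intervention group and 3.64 (SD 1.01) in the control group. It concludes: "A sample size of 49 achieved in each group, power 95% with a significance level (alpha) of 0.01". The total recruited is given as 98. The section does not say whether the test is one- or two-sided and makes no allowance for dropout. The randomisation section specifies equal groups, "following a 1:1 allocation ratio".

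The Data Analysis Procedure section gives a different significance level: "A p value less than and equal to 0.05 was considered as significant". It does not refer to the 0.01 used for sizing.

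**The concern.** The planned difference is 0.45 points and the larger SD is 1.01, so the standardised effect is moderate (about 0.57). A trial of 49 per group would not usually have 95% power for an effect of that size at an alpha as strict as 0.01. The inputs are all printed, so the claim can be tested directly.

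The stated power tells a reader how to weigh a non-significant result. A 95% figure implies that a true effect of the planned size would be missed only 1 time in 20. If the real figure is much lower, a null finding carries much less weight than the text suggests, and the error would pass into any report that repeats the sentence. The two alphas add a second inconsistency: a p value between 0.01 and 0.05 counts as significant in the analysis section but not at the level used for sizing.

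**Working it through.** **Inputs, all from the Sample Size section except where noted**

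- Difference: 4.09 − 3.64 = 0.45
- Sum of variances: 0.49² + 1.01² = 0.2401 + 1.0201 = 1.2602
- Root-mean-square SD: √(1.2602/2) = 0.794; standardised effect 0.45/0.794 = 0.567
- Allocation 1:1 (randomisation section), 49 per group
- Alpha 0.01 and power 95% as stated; alpha 0.05 from the Data Analysis Procedure section
- Sidedness is not stated, so both are shown

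**Step 1. Try to reproduce 49 per group**

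n per group = (SD₁² + SD₂²)(z_alpha + z_beta)² / difference²

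| Alpha | Sides | Power | Calculation | n per group |
|---|---|---|---|---|
| 0.01 | two | 95% | 1.2602 × (2.576 + 1.645)² / 0.2025 = 110.86 | 111 |
| 0.01 | one | 95% | 1.2602 × (2.326 + 1.645)² / 0.2025 = 98.14 | 99 |
| 0.05 | two | 95% | 1.2602 × (1.960 + 1.645)² / 0.2025 = 80.87 | 81 |
| 0.05 | one | 95% | 1.2602 × (1.645 + 1.645)² / 0.2025 = 67.35 | 68 |
| 0.05 | two | 80% | 1.2602 × (1.960 + 0.842)² / 0.2025 = 48.85 | **49** |

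The stated combination (first two rows) does not return 49. The last row does.

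**Step 2. Check whether another reading of the SDs rescues the claim**

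At alpha 0.01 and 95% power, per group:

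- SD 0.49 alone: 43 two-sided, 38 one-sided
- SD 1.01 alone: 180 two-sided, 159 one-sided
- Simple average of the SDs (0.75): 99 two-sided, 88 one-sided

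None gives 49. A one-sample formula with SD 0.794 at one-sided 0.01 and 95% power gives 49.07, but it is not valid for comparing two groups.

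**Step 3. Power that 49 per group provides**

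Standard error = √(1.2602/49) = 0.1604, so the expected test statistic is 0.45/0.1604 = 2.806. Normal-approximation power is Φ(2.806 − z_alpha). For example, two-sided 0.01 gives Φ(2.806 − 2.576) = 59.1%, and two-sided 0.05 gives Φ(2.806 − 1.960) = 80.1%.

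| Alpha | Sides | Normal approximation | Welch t (69.4 df) |
|---|---|---|---|
| 0.01 | two | 59.1% | 56.5% |
| 0.01 | one | 68.4% | 66.5% |
| 0.05 | two | 80.1% | 79.0% |
| 0.05 | one | 87.7% | 87.2% |

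No cell reaches 95%.

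**Step 4. Difference detectable with 95% power at 49 per group (two-sided)**

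- Alpha 0.01: (2.576 + 1.645) × 0.1604 = 0.68
- Alpha 0.05: (1.960 + 1.645) × 0.1604 = 0.58

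Both exceed the planned 0.45.

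**The case against.** The arithmetic is hard to dispute, but several points can be made for a more cautious statement.

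- *Sidedness.* The plan does not state it and the hypothesis is directional. This stands as a qualification: 59% is the two-sided figure and the one-sided figure is 68%. Neither is near 95%.
- *Two alphas.* Sizing at a stricter level than the one tested is not in itself an error, and the analysis section does set one decision threshold, 0.05. That is correct: success is not left undefined. The unexplained mismatch still needs to be reconciled.
- *Normal approximation.* For the t-test the plan names, power at two-sided 0.05 is 79.0% by Welch, and 51 per group would be needed to reach 80%. The corrected sentence should say which method it uses.
- *The planned test.* The analysis section applies Mann-Whitney, not the t-test, to perceived susceptibility. If the scores were normal with these SDs (an assumption, since the plan treats them as non-normal), simulation gives about 76% power at 0.05 and 53% at 0.01. This widens the gap from 95%.
- *Origin of 49.* The match with 80% power and two-sided 0.05 does not prove what was entered. One-sided 0.01 with 95% power gives 98.14 per group, so 98 might be a per-group figure read as a total. The documents cannot settle this, and the printed claim is false under either explanation.
- *Relevance.* The objectives concern knowledge and behaviour, while the calculation concerns perceived susceptibility, so it says little about power for the stated outcomes. This limits how far any power figure here carries, corrected or not.
- *Timing.* Recruitment is complete, so the sample cannot be changed. The false statement can still be corrected before it is repeated in a report.

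**Conclusion.** The concern holds. On the plan's own inputs, 49 per group does not give 95% power at alpha 0.01 under either sidedness or any two-sample reading of the SDs. At two-sided 0.01 the required number is 111 per group, more than twice the stated 49 (111/49 = 2.27).

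The chance of missing a true 0.45-point difference is about 20% (21% by Welch) at the two-sided 0.05 level used for analysis. At the stated 0.01 it is about 41% (44% by Welch) two-sided, or 32% one-sided. The text implies 5%. These figures assume the printed means and SDs, 1:1 allocation, complete follow-up of all 98 patients, and a comparison of means. Any dropout would lower power further. The statement is wrong as written and should be corrected.

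**What to change.** Replace the power statement in the Sample Size section with one that the inputs support. It should say that 49 per group gives about 80% power (normal approximation; 79% by Welch t) at two-sided alpha 0.05 to detect a 0.45-point difference in mean perceived susceptibility, with SDs of 0.49 and 1.01. Remove the 95% and 0.01 figures. State alpha 0.05, two-sided, in both the Sample Size and Data Analysis Procedure sections.

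Because recruitment is complete, mark the change as a correction of the calculation. It should not read as the rationale on which the trial was originally sized. If the OpenEpi entries are still available, check them and note what was entered.

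The cost is wording only. No patients are added, and neither the tests nor the 0.05 threshold change. The stated power becomes less favourable.

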## **Study Duration From date to date**

The study was conducted from July 2025 to December 2025, including participant recruitment, the delivery of the educational intervention, and the completion of post intervention assessments.

## **Inclusion Criteria**

- Adults aged 18-65 years with a confirmed diagnosis of T2DM
- Able to use WhatsApp for the study duration
- Able to read and write in Urdu

## **Exclusion Criteria**

- Edentulous
- Individuals diagnosed with life-threatening diseases such as advanced cancer, end-stage renal disease, or severe cardiac failure
- Diminished cognitive ability
- Radiotherapy in head and neck region.
- Planning to migrate during the study period.

## **Ethical Considerations**

Ethical approval was obtained from the Institutional Review Board (IRB) of Dow University of health sciences prior to data collection. (IRB-4057/DUHS/Approval/2025/294)

## **Data Collection Procedure**

Data were collected using a self-reported questionnaire delivered at two points: baseline (before intervention) and one-month post-intervention, to assess changes in oral health knowledge and behaviors.

At baseline, a detailed questionnaire was completed by all the participants. The intervention group then received educational training based on the HBM through WhatsApp videos, while the control group was provided with an educational brochure containing information related to oral health. Over a period of one month, participants were followed to monitor any changes.

1-month follow-up aligns with Mesbahi and Aleksejuniene's (2024) strategy, where an initial 5-week follow-up assessed the efficiency of the intervention(9). At the end of this period, the questionnaires were again completed by both groups.

